3.4.1 Demographics and baseline characteristics

Demographic and background data, initial amount of the filler applied, and occurrence of the Touch-up treatment with the amount of the filler applied will be summarized using descriptive statistical methods. Quantitative and continuous variables will be summarized by descriptive statistics and categorical data by frequency tables within each manufacturing site, C1 and HQ, separately and for the whole analysis population.

Page 16 of 21

Prior medications, coded using the WHO Drug Global Dictionary and previous cosmetic procedures on the face as well as medical history including MedDRA coding will be listed per subject.

3.4.2 Discontinuations and dropouts

Subjects discontinuing the study will be listed with the reason for discontinuation and last study day.

3.4.3 Performance analyses

3.4.3.1 Hypotheses

This is a non-comparative clinical investigation and does not entail formal hypothesis testing. All analyses will be done using descriptive statistics.

3.4.3.2 Statistical analyses

The performance analyses will be done in the Intent-to-treat population. Additionally certain analyses will be presented for the per-protocol population also to provide sensitivity analyses in the final analysis.

Individual NLF-SRS grades per visit will be calculated as the mean of grades assigned to the left and the right NLF, respectively, for descriptive summaries.

The improvement over Baseline in the NLF-SRS grade assessed by the investigator will be computed for each subject by subtracting the NLF-SRS grade obtained at each post-baseline time point from ipsilateral NLF-SRS grade obtained at Baseline. The individual improvement per visit will be calculated as the mean of both improvements in the left and the right NLF, respectively, for descriptive summaries.

The response rate will be calculated as the proportion of subjects with NLF-SRS improvement (i.e, reduction in NLF severity grade) of a \geq 1 point in both NLFs. The proportion of subjects with NLF-SRS improvement of \geq 2 points in both NLFs will be determined accordingly.

Two-sided 95% confidence intervals for the percentages of responders at various time points will be given for the proportions of the NLF-SRS improvements of ≥ 1 or ≥ 2 points, respectively using the large sample normal approximation. Also, two-sided 95% confidence intervals for the mean of individual NLF-SRS improvement at various time points will be calculated assuming normal distribution.

Summaries will be provided for the whole analysis population, as well as within each manufacturing site, C1 and HQ, separately.

Primary performance outcome measures

For the primary performance outcome measure, the percentage of responders with a \geq 1-point improvement over Baseline on the NLF-SRS based on investigator's live assessment at Week 24, the following will be given by manufacturing site and for the whole analysis population:

• percentage of responders with a ≥1-point improvement over Baseline on the 5-point NLF SRS, based on investigator's live assessment at Week 24 after initial treatment,

Secondary performance outcome measures

For secondary performance outcome measures the following will be given by manufacturing site and for the whole analysis population:

 percentage of responders with a ≥1-point improvement over Baseline on the 5-point NLF SRS, based on investigator's live assessment at Week 4, 36, 52 and optional at Week 65, 78 and 104 after initial treatment,

Page 17 of 21

• descriptive summary statistics for average change versus baseline in the NLF-SRS grade, evaluated by the investigator at Week 4, 24, 36, 52 and optional at Week 65, 78 and 104 after initial treatment,

Exploratory performance outcome measures

For exploratory performance outcome measures the following will be given for the whole analysis population:

- percentage of responders with a ≥2-point improvement over Baseline on the 5-point NLF SRS, based on investigator's live assessment at Week 4, 24, 36, 52 and optional at Week 65, 78 and 104 after initial treatment,
- percentage of subjects with aesthetic improvement using the 5-point GAIS (subjects who have been rated as "very much improved" or "much improved" or "improved"), based on investigator's assessment at Week 4, 24, 36, 52 and optional at Week 65, 78 and 104 after initial treatment, for each treatment location (right NLF, left NLF) separately and overall,
- percentage of subjects with aesthetic improvement using the 5-point GAIS (subjects who have been rated as "very much improved" or "much improved" or "improved"), based on subject's assessment at Week 4, 24, 36, 52 and optional at Week 65, 78 and 104 after initial treatment, for each treatment location (right NLF, left NLF) separately and overall,
- percentage of responders with a ≥1-point improvement over Baseline on the 5-point NLF SRS, based on evaluation by an independent reviewer of photographs for Week 4, 24, 36, 52 and optional at Week 65, 78 and 104 after initial treatment,
- descriptive summary statistics for extent of subject satisfaction with outcome of the treatment, as assessed by the Face-Q questionnaire "Satisfaction with Outcome" at Week 4, 24, 36, 52 and optional at Week 65, 78 and 104 after initial treatment,
- descriptive summary statistics for pain intensity, as evaluated by the subject using an 11point Numeric Pain Rating Scale (NPRS) immediately after the last injection and 15 min thereafter, at Day 0 and optional at Week 2.
- percentage of subjects having an aesthetic effect, based on the investigator's life assessment at Week 4, 24, 36, 52 and optional at Week 65, 78 and 104.

Subgroups by injection device and by injection technique for performance outcome measures For analyses by the injection device (needle, cannula) and by injection technique (retrograde,

bolus) the following will be given for the whole analysis population:

- percentage of responders with a ≥1-point improvement over Baseline on the 5-point NLF SRS, based on investigator's live assessment at Week 4, 24, 36, 52 and optional at Week 65, 78 and 104 after initial treatment,
- descriptive summary statistics for average change versus baseline in the NLF-SRS grade, evaluated by the investigator at Week 4, 24, 36, 52 and optional at Week 65, 78 and 104 after initial treatment

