#### Bolus technique:

The vertical supraperiosteal depot technique, where small depots of the filler (0.02-0.05 mL) are placed via serial vertical injections (2-3 mm apart) directly on the periosteum.

A minimum of 30 subjects should be treated either with the Retrograde technique or with the Bolus technique.

Lateral movements of the needle must be avoided since these may result in a fanlike dissection of the sub-epidermal plane, increasing the incidence of local AEs like bruising, swelling, redness, pain, or tenderness at the injection site.

The device should be injected slowly with the least amount of possible pressure for the same reason. If the needle or cannula is blocked, the pressure on the plunger rod should not be increased, but the injection stopped and the needle or cannula replaced.

If a larger volume of the filler is needed to achieve the correction, small volumes should be injected in two sessions, instead of high volumes in one session.

The injection must be stopped just before the needle or cannula is pulled out of the skin to prevent leakage of the device or placement too superficially in the skin.

The remainder of the investigational device from the same syringe after application to one fold can be used for the application to the other fold of the same subject at the same visit but not for any other subject or any other visit of the same subject.

In case of a vascular event, injection must be stopped immediately, and high dose hyaluronidase, massage and heat (gauze with hot water) should be applied. In addition, nitroglycerin paste may encourage vasodilatation. More details are provided in Section 4.2.

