#### 7.1 Sample size

Up to approx. 100 + 10 subjects with moderate to severe nasolabial folds will be randomized with a 1:1 allocation to the manufacturing sites C1 and HQ, in order to obtain the 24-week performance and safety data from approximately 50 of them in each manufacturing site. This sample size is considered appropriate for the clinical investigation and sufficient to provide robust estimations on performance and safety parameters in the study population. A sample size of approximately 50 allows a meaningful range estimation, the confidence interval, for the true proportion of success (reduction in NLF-SRS grades of  $\geq$ 1) at week 24. With a sample size of 50, a confidence level of (1-  $\alpha$ ) with  $\alpha$ =0.05 and an estimated proportion of 0.9 a two-sided 95% confidence interval for the true proportion using the large sample normal approximation is given through [0.817; 0.983]. Thus, in compliance with the study design, the true proportion is expected in the range of the confidence interval with an error probability of 5%.

A 'responder' is defined having at least  $\geq$  1 grade improvement as evaluated with the 5 point-validated NLF-SRS at week 24 relative to Baseline (Day 0) score on both sites. Individual NLF-SRS grades per visit will be assessed separately for the right and left NLF. A Response rate of 90% at week 24 is estimated.

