2.2 Sample size justification

Up to approx. 100 + 10 subjects with moderate to severe nasolabial folds will be randomized with a 1:1 allocation to the manufacturing sites C1 and HQ, in order to obtain the 24-week performance and safety data from approximately 50 of them in each manufacturing site. This sample size is considered appropriate for the clinical investigation and sufficient to provide robust estimations on performance and safety parameters in the study population. A sample

page 9 of 21

size of 50 allows a meaningful range estimation, the confidence interval, for the true proportion of success (reduction in NLF-SRS grades of \geq 1) at week 24. With a sample size of 50, a confidence level of (1- α) with α =0.05 and an estimated proportion of 0.9 a two-sided 95% confidence interval for the true proportion using the large sample normal approximation is given through [0.817;0.983]. Thus, in compliance with the study design, the true proportion is expected in the range of the confidence interval with an error probability of 5%.

Page 10 of 21

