3.4 Statistical methods

The final statistical analysis will be done after completion of the investigation by all subjects. The interim analysis will be done after all subjects have completed the Week 24 study procedures.

In general, collected data will be listed and descriptive statistics will be performed, with all repeating measurements being tabulated by visit.

For qualitative and discrete variables, the total number of observations, frequency and percentages of categories / scores will be calculated.

Quantitative and continuous variables will be described by declaring descriptive summary statistics (number of observations, the mean value, standard deviation, minimum, first quartile, median, third quartile, and maximum).

Two-sided 95% confidence intervals will be calculated assuming normal distribution, if not stated otherwise.

The primary and secondary performance analysis and the safety analysis will be done for each manufacturing site, C1 and HQ, separately and for the whole analysis population. The exploratory performance analysis will be done for the whole analysis population, ITT and PP respectively, only.

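### The 95% intervals for responder rates use the Wald formula, which at the planned 50 per site and 90% response covers the true rate about 88% of the time and, when it misses, nearly always overstates it

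*SAP*

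**What the plan says.** SAP 3.4.3.2 states: "Two-sided 95% confidence intervals for the percentages of responders at various time points will be given" for improvements of ≥1 and ≥2 points, "respectively using the large sample normal approximation". The summaries are given overall and for each manufacturing site. SAP 3.4 sets the default for other intervals: "Two-sided 95% confidence intervals will be calculated assuming normal distribution, if not stated otherwise". No exact or score interval is named anywhere, and there is no fallback for proportions near 0% or 100%.

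The sample size rests on the same formula. SAP 2.2 aims for "performance and safety data from approximately 50 of them in each manufacturing site" and uses "an estimated proportion of 0.9 a two-sided 95% confidence interval", giving [0.817; 0.983]. It concludes that "the true proportion is expected in the range of the confidence interval with an error probability of 5" percent. Protocol 7.1 carries the same calculation and conclusion and adds: "A Response rate of 90% at week 24 is estimated".

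Protocol 5.2 and SAP 3.4.3.1 rule out formal hypothesis testing. The protocol synopsis treats the responder count as binomial but names no interval method.

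**The concern.** The Wald interval is centred on the observed proportion and takes its width from that same proportion. When the true rate is near 1 and n is moderate, a sample with too many responders gives an interval that is both too high and too narrow, so it excludes the truth more often than the nominal level allows. The planned rate of 90% and about 50 subjects per site fall in this region.

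With no test, the Week 24 interval is the trial's only inferential result on the primary endpoint and its only quantitative sample-size justification. If its real error rate is well above 5%, the stated precision is wrong. If the misses are mostly in one direction, the lower limit tends to be too high, and that is the figure a reader uses to judge how low the response rate could plausibly be. Protocol 3.3 says the data should support approval, so the limit will be read.

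**Working it through.** **Inputs.** n=50 per site, p=0.90, two-sided 95% (SAP 2.2, protocol 7.1). About 100 subjects overall, up to about 110 randomised (protocol 7.1). Sensitivity value p=0.941, the per-protocol Week 24 response in the earlier post-market study (protocol 3.2).

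**Reproducing the plan's interval.** Wald: p ± 1.96·√(p(1−p)/n) = 0.9 ± 1.96·√(0.09/50) = 0.9 ± 0.0832 = [0.8168; 0.9832]. This matches [0.817; 0.983]. The continuity-corrected version gives [0.807; 0.993] and does not match, so the plan means the plain Wald interval.

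**Exact coverage.** For a given n and true p, add the Binomial(n, p) probabilities of every count x whose interval contains p. At n=50 and p=0.90:

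- x from 40 to 47: the interval contains 0.90.
- x=48 (interval from 0.906), 49 (from 0.941) and 50 ([1; 1]): wholly above 0.90. Probability 0.0779 + 0.0286 + 0.0052 = 0.1117.
- x ≤ 39 (at x=39 the upper limit is 0.895): wholly below 0.90. Probability 0.0094.
- Coverage = 1 − 0.1117 − 0.0094 = 0.8789. The error is 12.1%, not 5%, and 0.1117/0.1211 = 92% of misses overstate the rate.

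**Other settings.**

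| n | true p | Wald coverage | wholly above p | wholly below p | Wilson coverage | Clopper-Pearson coverage |
|---|---|---|---|---|---|---|
| 50 | 0.90 | 87.9% | 11.2% | 0.9% | 97.0% | 97.0% |
| 50 | 0.941 | 80.0% | 19.8% | 0.2% | 97.3% | 99.2% |
| 55 | 0.90 | 91.5% | 7.7% | 0.7% | 93.4% | 96.0% |
| 100 | 0.90 | 93.2% | 5.8% | 1.0% | 93.6% | 95.6% |
| 100 | 0.941 | 93.3% | 6.1% | 0.6% | 95.0% | 96.9% |
| 110 | 0.90 | 91.9% | 6.8% | 1.3% | 96.3% | 97.6% |
| 110 | 0.941 | 88.9% | 10.5% | 0.5% | 96.1% | 97.7% |

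At p=0.90, Wald coverage for n from 45 to 55 ranges from 86.4% (n=48) to 95.0% (n=47); for n from 48 to 52 it is 86.4% to 89.1%.

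Because of this oscillation, the mean over p=0.85 to 0.95 is a fairer summary. Wald averages 90.6% at n=50, with 8.6% wholly above the truth against a nominal 2.5% per tail, and 92.7% at n=100. Wilson averages 95.4% and 95.2%.

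**Impossible limits.** At n=50 the upper limit exceeds 1 for x=47, 48 and 49. At p=0.90 that has probability 0.1386 + 0.0779 + 0.0286 = 24.5%; at p=0.941 it is 61.1%. For 47/50 the interval is [0.874; 1.006]. For 50/50 it is [1; 1], where Clopper-Pearson gives a lower limit of 0.929.

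**Effect on reported limits.**

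| Result | Wald | Wilson | Clopper-Pearson |
|---|---|---|---|
| 45/50 | [0.817; 0.983] | [0.786; 0.957] | [0.782; 0.967] |
| 47/50 | [0.874; 1.006] | [0.838; 0.979] | [0.835; 0.987] |
| 90/100 | [0.841; 0.959] | [0.826; 0.945] | [0.824; 0.951] |

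**The case against.** The strongest reply is that nothing in the trial turns on this interval. There is no hypothesis, margin or success rule, the two manufacturing sites are presented descriptively, and the point estimate is unaffected. The method is disclosed and used consistently, and a reader with the counts could calculate a better interval. All of that is true: no pass/fail decision changes, and the planning calculation contains no arithmetic error. But the plan does more than choose a method. It states a 5% error probability, and that statement is false at the plan's own inputs. The absence of a test makes the interval more important, because nothing else expresses uncertainty about the primary endpoint.

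A second reply is that 88% and 80% are low points of an irregular curve. This stands in part. At p=0.941, n=49 gives 94.2%; at p=0.90, n=47 gives 95.0% and n=105 gives 95.0%. The whole-population interval suffers less, and at n=100 with p=0.90 Wilson (93.6%) is hardly better than Wald (93.2%), although its misses are far less lopsided. The averages remain below 95% at both sizes, and the per-site sizes the plan aims for, about 50, are where coverage is poor. The 94.1% is a per-protocol result from an earlier study, so it serves only as a sensitivity value.

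Third, the subgroup evidence is weak. Protocol 6.2.2 says "A minimum of 30 subjects should be treated either with the Retrograde technique or with the Bolus technique", which is an ambiguous recruitment floor, and the subgroup lists in the SAP do not themselves mention intervals. At n=30 and p=0.90 the Wald interval would cover 80.9%, but this is an illustration and the conclusion does not depend on it.

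**Conclusion.** The concern holds. At the planned n=50 and 90% response, the nominal 95% interval has 87.9% exact coverage. Its error probability is 12.1% where the plan states 5%, and 92% of the misses place the interval above the true rate. Averaged over true rates from 0.85 to 0.95, coverage is 90.6% per site and 92.7% for 100 subjects. The damage is to the stated precision and to the lower limit, which for 45/50 is 3.0 points above Wilson (0.817 against 0.786) and 3.5 points above Clopper-Pearson (0.782). For 90/100 the gap to Wilson is about 1.6 points (0.841 against 0.826). It does not affect a type I error or a success decision, because the trial has neither.

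The result assumes independent subjects with a common response probability within the group analysed, the binomial model the protocol synopsis adopts, and subject numbers close to plan. The exact coverage figure depends on the n and p realised.

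**What to change.** - **SAP 3.4.3.2:** replace the large-sample normal approximation with one named method, Wilson score or Clopper-Pearson, for every responder proportion (≥1 and ≥2 points, all visits, each manufacturing site and overall, and any subgroup interval reported). Wilson holds about 95% on average; Clopper-Pearson does not fall below 95% but is somewhat wider.
- **SAP 3.4:** limit the normal-distribution default to means, so that it cannot bring the Wald interval back for other proportions.
- **SAP 2.2 and protocol 7.1:** restate the planning interval for 45/50 as [0.786; 0.957] (Wilson) or [0.782; 0.967] (Clopper-Pearson), and delete the 5% error statement attached to the Wald interval.
- **Timing:** make the change before the Week 24 interim analysis, which reports the primary endpoint, so that the method is not chosen with results in view.

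The cost is a wording change in two documents and a standard SAS option. No subjects, visits or data are added. The planning lower limit becomes 3.0 to 3.5 points less favourable.

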3.4.4 Safety analyses

The safety analyses will be done in the safety population.

Safety will be evaluated by tabulations of applied volume of the device and AEs.

3.4.4.1 Applied volume of the device

The applied volume of the study device will be summarized by the injection volume applied to achieve optimal aesthetic result with saypha® VOLUME at initial and (optimal) touch-up treatment, respectively. Descriptive statistics will be presented by visit, treatment area and center separately and overall.

Page 18 of 21

3.4.4.2 Adverse events

Adverse events will be coded using the MedDRA dictionary Version 22.1 from September 2019 and listed by subject.

Summaries of AEs will be provided for seriousness, severity, causal relationship to the device and causal relationship to procedure. The summaries will be given for all AEs and regarding TEAEs by center, by manufacturing site and for the whole safety population and for local and non-local, separately.

The incidence of TEAEs will be summarized by preferred term and system organ class, and by seriousness, severity and by causal relationship to the device or procedure. The incidence will be given for all TEAEs, as the proportion of subjects with any TEAE in the safety population.

Incidences by local and non-local TEAE will be determined as the proportion of subjects having an TEAE accredited to a test field in the safety population of subjects exposed to the IMD.

At each level of summarization (system organ class or preferred term) subjects are only counted once, under the greatest reported seriousness, severity or closest relation

If appropriate, listings of ADEs, SAE, SADEs, device deficiencies and subjects who prematurely discontinued the investigation due to AEs will be given.

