# Touch-up treatment is optional (at investigator's discretion, if full correction was not achieved after initial treatment).

• Telephone communication approximately 24 hours post-administration in order to monitor adverse events. In case of AEs an unscheduled visit should take place.

- $^{\Omega}$  To be performed only if Touch-up treatment occurred
- a Includes date of birth, sex, and race
- b All medication taken by the subject within the previous 10 days
- c Performed by the investigator using the Nasolabial Folds Severity Rating Scale (NLF-SRS); the severity of the left and the right fold will be separately graded
- d In females of child-bearing potential only, including women who are postmenopausal for less than 12 months
- e Evaluated by the subject immediately after injection and approximately 15 min. thereafter using an 11-point Numeric Pain Rating Scale
- f Evaluated by the investigator using the Global Aesthetic Improvement Scale (GAIS)
- g Evaluated by the subject using the FACE Q Satisfaction with Outcome
- h To be collected throughout the investigation, from beginning of the treatment until the last visit, in order to identify potential adverse events post-administration an safety evaluation after 15 minutes needs to take place.

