#### 6 Design of the clinical investigation

#### 6.1 Design description

СГОП

The present investigation is designed as a prospective, non-comparative, randomized, multicenter study. As justified in Section 3.3, this type of design is considered appropriate in view of the purpose and objectives of the study.

The investigation will consist of 11 visits (the three last visits are optional): the baseline (Day 0) visit, which will entail informed consent, screening assessments, the treatment, and early post-treatment assessments, telephone communication approximately 24 hours post-administration for monitoring of adverse events and follow-up visits at Week 2, 4, 24, 36, 52, 65 (optional), 78 (optional) and 104 (optional) after the treatment. Procedures to be performed at each visit are specified in Table 1. Schedule of procedures and events, which is located on page 11 and in section 6.

In case it is observed by the investigators that at a given visit no aesthetic effect is any more visible in approximately 75 % of the subjects, the study can be terminated at an earlier time point, but not before week 52.

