#### 6.3 Subjects

#### 6.3.1 Number of subjects and duration of the clinical investigation

Approximately 100 + 10 subjects with moderate to severe nasolabial folds will be enrolled and treated with the investigational device in order to obtain the Week 24 performance data in at least 100 subjects (approximately 50 of them in each manufacturing site). Approximately 10 drop outs are estimated.

Each subject will participate in the study for maximum of 104 weeks. Considering the anticipated recruitment period of 3 months, the total expected duration of the clinical investigation will be

maximum of 27 months. Recruitment halts due to COVID-19 pandemic lead to the prolongation of the recruitment period and the extension of the total duration of the clinical investigation.

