#### 6.4.7 Assessment of aesthetic effect

The investigator will assess whether the aesthetic effect is still present in the subject. A liveassessment of the treated areas will be performed and the treated areas will be compared to the subject's photographs obtained at the Baseline Visit. The presence of the aesthetic effect will be recorded as either "Yes" or "No" in the subject's medical record and in the eCRF. If a subject no longer has an aesthetic effect as of Week 52, this may prematurely lead to the termination of the clinical examination of the respective subject.

In this case new injections can be placed at previously injected locations.

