#### 6.4.11 Safety monitoring

The safety of the investigational device will be monitored throughout the investigation, from Day 0/visit 1 until the final visit (visit 9). AEs will be collected at each visit. In addition, the subjects will be instructed to immediately contact the investigator by phone in case of occurrence of any untoward event between the visits. The procedure for collection, recording and reporting of AEs is described in Section 14.

In order to identify potential adverse events post-administration a safety evaluation after 15 minutes needs to take place.

In case a scheduled on-site visit cannot take place due to COVID-19 pandemic, the investigator should attempt to postpone the visit or make a safety-phone call to monitor the safety of the investigational device.

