1.2.4 Safety endpoints

Endpoints to evaluate the safety and long term safety of the device are:

- Occurrence and frequency of adverse events within each manufacturing site, C1 and HQ, separately and for the whole analysis population
- Occurrence and frequency of adverse events within each subgroup defined by the injection device, needle and cannula, respectively.

Concomitant medications documented throughout the study and device deficiencies will be reported.

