3.3 Analysis sets

All safety analyses will be based on the Safety analysis set, defined as all subjects who received the IMD.

The Intent-to-Treat (ITT) population is defined as all subjects who received the IMD and have at least one post-treatment assessment. The ITT population will be the primary analysis population for analyses of performance of the investigational device and of aesthetic effects in interim and in final analysis.

Page 15 of 21

The assignment of subjects to the safety analysis set and to the ITT population will be done prior to the interim analysis after Week 24.

A Per-Protocol (PP) population is defined to provide sensitivity analyses in the final analysis. The PP population comprises all subjects in the ITT population, who completed the Week 24 assessment without any major CIP deviations (i.e. CIP deviations that interfere with the performance evaluation or the aesthetic effect evaluation).

Subjects will be excluded from the PP population,

- who violated any inclusion/exclusion criteria during the course of the study;
- who's primary performance outcome measure, the ≥1-point improvement over Baseline on the NLF-SRS based on investigator's live assessment at Week 24 is missing, except it is a missing assessment for treatment related reason, e.g. discontinuation of assessments due to adverse events at least possibly related to IMD or due to lack of efficacy;
- who received any medication or procedure interfering with the performance or aesthetic effect evaluation at Week 24.

Prior to the final statistical analysis, other additional criteria may be added to the list to accommodate for unforeseen events that occurred during the conduct of the trial that result in noteworthy study protocol violations.

The assignment of subjects to the PP population will be finalized within a data review meeting for the final analysis.

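### The only planned adverse-event incidence divides by all treated subjects although follow-up may end anywhere from Week 52 to Week 104, so late-onset terms may be understated

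*SAP*

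**What the plan says.** **Incidence measure.** SAP 3.4.4.2 summarises treatment-emergent adverse events by system organ class, preferred term, seriousness, severity and causality. "The incidence will be given for all TEAEs, as the proportion of subjects with any TEAE in the safety population". For the denominator, SAP 3.3 states: "All safety analyses will be based on the Safety analysis set, defined as all subjects who received the IMD". Neither document plans a summary of follow-up time, incidence by onset interval, numbers under observation, person-time rates or a time-to-event estimate.

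**Aim.** The Synopsis lists long-term safety among the objectives. SAP 1.2.4 introduces its adverse-event endpoints with "Endpoints to evaluate the safety and long term safety of the device are".

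**Length of follow-up.** Protocol 6.3.1: "Each subject will participate in the study for maximum of 104 weeks". The last three visits (Weeks 65, 78 and 104) are optional. For the single subject, Protocol 6.4.7 adds: "If a subject no longer has an aesthetic effect as of Week 52, this may prematurely lead to the termination of the clinical examination". For the whole study, once about 75% of subjects show no effect, Protocol 6.1 says "the study can be terminated at an earlier time point, but not before week 52". Protocol 6.3.1 also estimates about 10 drop-outs.

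**End of adverse-event collection.** Protocol 6.4.11 monitors safety "from Day 0/visit 1 until the final visit (visit 9". Footnote h to Table 1 says of adverse events: "To be collected throughout the investigation, from beginning of the treatment until the last visit". Table 1 itself, Protocol 6.1.6.5 and SAP 2.3 schedule adverse events up to Visit 11.

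**The concern.** A proportion of all treated subjects is a fair estimate of risk to a given time only if nearly everyone is observed to that time. Here observation after Week 52 can differ two-fold between subjects, and one reason for ending it is loss of effect. The protocol expects the effect to persist 6 to 12 months (4.1) and the device to last up to 9 months (2.1). Loss of effect by Week 52 is therefore plausible for many subjects.

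Early injection-site events are little affected, because they occur while almost everyone is still followed. Late-onset events are different. Protocol Table 2 names granuloma, nodules and implant migration among the possible effects of these fillers. If such events arise in the second year, they are counted only in those still followed but divided by everyone treated. A reader of the preferred-term table cannot tell how many subjects stood behind a low late count, or behind a zero.

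**Working it through.** **The plan's own figures.** The plan gives no figure for adverse-event incidence or its precision. Its one computed figure, the Week 24 responder interval in SAP 2.2, reproduces: 0.9 ± 1.96 × √(0.9 × 0.1 / 50) = 0.9 ± 0.083, or [0.817; 0.983]. It does not bear on this point.

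**Inputs**
- Treated: 110 (Protocol 7.1 and SAP 2.2, about 100 + 10).
- Drop-outs: 10 (Protocol 6.3.1), assumed lost before Week 52, which leaves 100.
- Share *f* of those 100 who stop at Week 52: not in the documents. Assumed 0, 25%, 50% and 74%. The last lies just below the study-level trigger of about 75%.
- True risk *q* of a late-onset event between Weeks 52 and 104: not in the documents. Assumed 2%, 5% and 10%.
- Those who stop are assumed to have the same risk as those who stay, and those who stay are followed to Week 104.

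**Late-onset events.** Expected crude proportion = 100 × (1 − *f*) × *q* / 110. Its ratio to the true risk is 100 × (1 − *f*) / 110, so *q* cancels.

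| *f* | Still followed | Ratio to true risk | Crude, *q* = 2% | Crude, *q* = 5% | Crude, *q* = 10% |
|---|---|---|---|---|---|
| 0 | 100 | 0.91 | 1.8% | 4.5% | 9.1% |
| 25% | 75 | 0.68 | 1.4% | 3.4% | 6.8% |
| 50% | 50 | 0.45 | 0.9% | 2.3% | 4.5% |
| 74% | 26 | 0.24 | 0.5% | 1.2% | 2.4% |

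Subjects who stop at Week 65 or 78 instead contribute part of the window, so their effect is milder.

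**Any-event percentage.** Assume that 50% of subjects have an early event and that the late risk is 5%. Complete follow-up gives 0.50 + 0.50 × 0.05 = 52.5%. With *f* = 74% the crude figure is 0.50 + 0.50 × 0.05 × 26/110 = 50.6%. With 30% early events the pair is 33.5% and 30.8%; with 70% it is 71.5% and 70.4%.

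**A zero count.** If no late event is seen, the exact one-sided 95% upper bound is 1 − 0.05^(1/*n*). This gives 2.7% for *n* = 110, 5.8% for *n* = 50 and 10.9% for *n* = 26. The plan does not promise such a bound. The figures show how much the number actually followed matters to the reading of a zero.

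**End of collection.** Visit 9 is Week 65. Protocol 6.1 plans 11 visits, so Visit 9 is not the last one. Table 1, its footnote h, Protocol 6.1.6.5 and SAP 2.3 agree with each other and not with 6.4.11.

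**The case against.** Several arguments on the other side have force.

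- **Understatement is not certain.** The individual stop is permitted, not required. If the whole study ends at one visit, follow-up is nearly equal and the crude proportion is fair up to that visit. The SAP also sets no time horizon for long-term incidence. This stands: a reader might infer that late risk *is* understated, but the documents support only that it *may* be, relative to Week 104.
- **The sentence quoted from 3.4.4.2 is barely affected.** It defines the any-event proportion, which early injection-site events probably dominate. This stands. However, the same section tabulates incidence by preferred term, and a late-onset term carries the full effect.
- **The listings already hold the information.** Start dates are recorded (Protocol 14.3), discontinuations are listed with last study day (SAP 3.4.2), and the interim analysis reports all safety tables at Week 24 (SAP 4). This is true, and it is why the fix is cheap. Listings still leave the reader to rebuild the denominator.
- **The sites are randomised.** One might infer a biased display of C1 against HQ. Allocation is 1:1, one stopping rule serves both groups and no test is planned. The documents give no reason to expect different follow-up.
- **Subject-year rates have their own fault.** Events cluster soon after injection, so a rate pooled over all follow-up falls as follow-up lengthens. This stands and shapes the fix.

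A reader might also take 6.4.11 to mean that adverse-event collection ends at Week 65. The other passages contradict that, so it is an unresolved inconsistency and not a settled rule.

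**Conclusion.** The point holds for late-onset terms and as a possibility. The sole incidence measure ignores length of follow-up, the plan allows that length to vary from Week 52 to Week 104, and long-term safety is an aim. Under the assumed stopping shares of 25%, 50% and 74%, the crude figure would be about 0.68, 0.45 and 0.24 of the true Week 52 to 104 risk; with only the 10 drop-outs lost it would be 0.91. These ratios do not depend on the event rate. They do rest on stopping shares that the documents do not give, and on stopping being unrelated to risk. The any-event percentage moves by roughly one to three points in the examples, even at the highest stopping share. The primary endpoint is untouched. The Visit 9 wording is a separate inconsistency and should not be used as evidence of biased incidence.

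**What to change.** In SAP 3.4.4.2, keep the crude table and add the following, by manufacturing site and overall:

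1. A summary of follow-up time per subject.
2. Incidence of treatment-emergent events by onset interval (Day 0 to Week 24, Week 24 to 52, after Week 52), by preferred term, with the number still under observation as denominator.
3. If subject-year rates are shown, give them within each interval and not pooled.
4. A note that stopping depends on loss of effect, so censoring may be informative. Interval denominators do not remove that.

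The cost is one extra table from visit dates and event start dates already collected.

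Separately, reconcile the final visit named in Protocol 6.4.11 with Table 1, footnote h, Protocol 6.1.6.5 and SAP 2.3, so that sites have one statement of how long adverse events are collected. This is an editorial correction.
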